# STUDY PROTOCOL

## Project Summary

### I. Rationale

With the use of combined antiretroviral therapies, people with HIV infection now live longer than ever before. However, the burden of non-AIDS related health problems such as cardiovascular diseases and cancers on people living with HIV/AIDS has considerably increased, which undermines the health of those living with HIV [1-3]. Smoking is one of the major contributing factors to these health problems. Rates of cigarette smoking are substantially higher among people living with HIV than the general population: 40-75% versus 19% [2]. HIV positive women smokers have a 36% higher risk for developing AIDS and a 53% higher mortality when compared to nonsmokers with HIV/AIDS [2]. However, the rates of abstinence achieved by the existing smoking cessation interventions for this group are very modest, hovering around 6-9% [e.g., 4, 5]. These rates are substantially lower than the rates (e.g., 16-30%) obtained from the general smoker population [6]. There is thus an urgent need to develop a smoking cessation intervention that is effective for women living with HIV, which will promote and protect women's health and their wellbeing.

The HIV-related measures (instruments) used in this study identify demographic characteristics, attitudes, beliefs, and behaviors. Each of the measures is selected to collect data that affect personal health (secondary and tertiary levels). For example, stigma measures assess the degree of personalized (or self) stigma, HIV disclosure concerns, negative self-image, and concern with public attitudes toward people with HIV, which may be related to health promotion and wellness efforts, such as smoking cessation. There is empirical evidence that women perceive more HIV-related stigma than men, and those who have high perceived HIV-related stigma are less likely to disclose their HIV status to others, to seek treatment and to adhere successfully to their medication [4]. The demographics and all other instruments were chosen and reviewed by the Massachusetts Department of Public Health Office of HIV/AIDS and used successfully in a randomized controlled trial (RCT) completed by [name] [7].

The smoking-related measures are chosen because they provide valuable information to tailor cessation intervention components to the specific needs of a person, based on one's smoking behavior and history of smoking cessation treatment. "Self-efficacy" has been identified as the only variable that significantly mediates the effect of smoking cessation intervention on abstinence [e.g., 8, 9]. There is ample evidence that people with depression and anxiety are less likely to succeed in smoking cessation [e.g., 10, 11]. We also include depression and anxiety measures to screen women who may have clinical depression or anxiety. They will be strongly urged to seek treatment for the condition. Of note, [name] is a licensed psychiatric advance nurse practitioner and those who earn a score of 16 or higher on the depression measure or 8 or higher on the Generalized Anxiety Disorder (GAD)-7 Scale will be interviewed for the diagnosis of depressive or anxiety disorder, respectively. If they meet the diagnostic criteria for any of the disorders based on the DSM-V, they will be excluded. All of the measures have been successfully used in previous smoking cessation studies by [name] [e.g., 12, 13].

### II. Background Information

[name] completed a smoking cessation intervention for Korean American women and is now preparing manuscripts for publication. She found that women with HIV and AIDS have many similarities with Korean American women in terms of their reluctance to seek smoking cessation treatment due to perceived stigma, and their preference for telephone counseling rather than in-person counseling [4, 5, 14]. Furthermore, similar to the low success rate of abstinence found among people with HIV infection, the rate of abstinence among Korean American women had been low (e.g., 5%) relative to their male counterparts (e.g., 17%) [15]. On the other hand, [name] videoconferencing smoking cessation intervention yielded an abstinence rate (28-30%), higher than

what has been reported for this population in previous studies [16], although findings are preliminary due to the nature of a pilot study. In [name] pilot trial, the smoking cessation interventions were tailored to the needs of Korean American women and the counseling is relatively intense (eight weekly 30-minute sessions) compared to the usual telephone counseling (four to six weekly 10-15 minute sessions). A meta-analysis of smoking cessation studies with the general US population revealed that high-intensity counseling support is more important for women than for men [17]. Thus, it is believed that if smoking cessation interventions are tailored to the specific needs of women with HIV and the cessation counseling is intense (e.g., eight weekly 30 minute sessions), women with HIV may achieve an abstinence rate that is higher than the rates reported in the literature [4, 5].

### III. Methodology.

The proposed study is a 2-arm parallel-group RCT of a smoking cessation intervention with 50 English-speaking women who have been diagnosed with HIV infection. Participants will be randomized at a ratio of 1:1 to either the video arm (n = 25) or the telephone arm (n = 25). The randomization will be based on computer-generated random numbers (<http://www.randomizer.org/>). The numbers will be written in a color-coded paper (the video arm = red and the control arm = blue). These papers will be placed in an envelope in order, which will be open right after the completion of the baseline assessment. Both arms will have eight weekly individualized counseling sessions and each session will be 30 minutes long. The study is conducted to determine the acceptability and feasibility of a videoconferencing smoking cessation intervention for women with HIV. It is also being conducted to estimate the effect of the videoconferencing smoking cessation intervention on abstinence compared with telephone counseling cessation intervention for women with HIV.

#### Recruitment Procedures

Participants will be recruited through the Sistah Powah Group, a group of women living with HIV whose purpose is to advance HIV prevention (primary, secondary, and tertiary prevention) and assist other HIV positive women in managing their co-morbidities through care engagement (e.g., ex-smoking behaviors). We will also contact the local HIV AIDS Service Organizations (ASOs) by contacting leaders at each area personally and asking them to forward our email message (see below in Box 1) or through, explaining the study and offering fliers to be shared with clients or posted at their organizations. For example, Dimock Health Center, Boston Living Center, Multicultural AIDS Coalition, Massachusetts Department of Health Office of HIV/AIDS, Fenway Health Center, AIDS Action, AIDS Alabama, University of Mississippi Medical Center, and HOCC (Healing Our Community Collaborative).

In addition, the following will be posted in online communities of people with HIV infection (e.g., HIV/AIDS Tribe and +supportgroups).

#### Box 1 Online Posting Sample

Who: All Women living with HIV infection who want to quit smoking.

Study Title: **Smoking Cessation Intervention for Women with HIV**

Contact Information: Please call [name] **[contact]** or [name] **[contact]** for more information AND eligibility.

The study is conducted at the University of Boston and the intervention is provided via phone calls. Visa gift cards (\$25-50) will be provided at each data collection point.

Anyone interested will be asked to contact the research team ([name] or [name]). Prior to the screening interview, a verbal consent (see the verbal consent form attached) will be obtained. If the caller is determined to be ineligible or refuses to participate, all data collected will be shredded immediately and will not be used in the study. Screening data for those who agree to participate but fail to provide a written consent form within two weeks from the screening interview will also be shredded. The screening data will be transferred to baseline assessment datasheet only after the caller provide a signed consent form. Then, the paper containing screening data will be shredded.

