Women who answer as above will be recruited into the study. They will be informed about the purpose and procedure of the study and then will be given time to ask questions if they have any. Once all questions being answered, [name] (or [name]) will ask them to provide the following contact information: mailing address, e-mail address, at least two connected telephone lines (the participant’s cell phone, home phone or a third phone). [name] (or [name]) will inform that they will be randomly selected to receive smoking cessation counseling either via a video call such as Face-time, Skype and Tango or by telephone. Individuals who are determined to be ineligible will be explained why they are not eligible for the study.

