Study Title: Smoking Cessation Intervention for Women Living with HIV
NCT NO: NCT02898597

January 31, 2017

Data Analysis Plan

Data will be reviewed prior to data entry and entered by a research coordinator, which will be double-checked for errors or completeness by a third person. Data will be analyzed using Stata 14 (Stata Corp LP, College Station, TX, USA). Intention-to-treat analytic strategy will be used for cessation outcomes with missing values. The primary outcome of the study will be a 6-month prolonged abstinence. Its secondary outcomes will include 7-day point prevalence abstinence at each follow-up (1, 3, and 6 months post-quit), time to the first lapse, time to relapse, recovery rates from smoking relapse as well as changes in self-efficacy, depressive symptoms, and anxiety symptoms between the two treatment conditions and over time (baseline and 3- and 6-month follow-ups).

Specific aim 1: test the feasibility and acceptability of a videoconferencing smoking cessation intervention for women with HIV.

Recruitment and retention rates will be recorded per month throughout the study period. Any barriers to the recruitment and retention will be explored. Reasons for those who are eligible but decline to participate in the study will be recorded. Attrition rates will be compared by intervention condition and abstinence status at each follow-up. All participants will be asked to complete an exit survey, rating their overall satisfaction with the intervention that they have received.

Specific aim 2: establish a preliminary effect size of the videoconferencing smoking cessation intervention on 6-month prolonged abstinence compared to the telephone-based smoking cessation intervention.

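### The Box 1 recruitment text describes a phone intervention and omits video and randomisation, so Aim 1 recruitment and refusal data need a cautious reading

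*Protocol*

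**What the plan says.** The Protocol's Methodology section gives the purpose: "The study is conducted to determine the acceptability and feasibility of a videoconferencing smoking cessation intervention for women with HIV". It also sets the allocation: "Participants will be randomized at a ratio of 1:1 to either the video arm (n = 25) or the telephone arm (n = 25").

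The Recruitment Procedures section gives Box 1 two uses. Leaders of local HIV service organisations are approached, with the team "asking them to forward our email message (see below in Box 1"), and "the following will be posted in online communities of people with HIV infection". Other channels do not depend on Box 1: "Participants will be recruited through the Sistah Powah Group", and fliers are offered whose wording is not shown.

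On the mode of delivery, Box 1 says only this: "The study is conducted at the University of Boston and the intervention is provided via phone calls". It does not mention random assignment.

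Both modes are disclosed later. The text after the screening script has eligible callers told that they will be randomly selected for "smoking cessation counseling either via a video call such as Face-time, Skype and Tango or by telephone". The Informed Consent section says that the consent form names videoconferencing or telephone sessions.

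Under Specific aim 1 of the SAP, "Recruitment and retention rates will be recorded per month throughout the study period". The plan there is also to explore barriers, record why eligible women decline, compare attrition by arm and by abstinence status, and run an exit survey on satisfaction.

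**The concern.** Aim 1 asks whether video counselling is feasible and acceptable. Part of its evidence is how many women come forward and why some eligible women refuse. An advertisement that offers phone calls alone describes something different from the trial that women are asked to join.

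Two losses of information could follow. A woman attracted by video but not by telephone has no reason to call, and nothing in the plan counts her. A woman who calls expecting telephone counselling and withdraws on hearing of video may be declining video itself, or may be reacting to an offer that changed during the call. Her refusal does not distinguish the two.

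The wording cannot easily be excused as loose usage. The Protocol's own disclosure to callers sets a video call against the telephone as alternatives.

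**Working it through.** The documents give no response, refusal or dropout counts and no feasibility threshold, so there is no figure of the plan's to reproduce. The check sets the steps of recruitment side by side.

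**Share of women affected by the omission.** From the Methodology section, video n = 25 and telephone n = 25. Share assigned to video = 25 / (25 + 25) = 50%. This is the allocation ratio, not the size of any effect of the posting.

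**What a woman knows at each step.**

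| Step | What she is told about mode | Source |
|---|---|---|
| Reads forwarded e-mail or online post | Phone calls only | Protocol, Box 1 |
| Verbal consent before screening | Not known; the form is not in the reviewed text | Protocol, text after Box 1 |
| Screening questions | Access to a telephone and an Internet-connected computer is asked; willingness to use video is not | Protocol, screening script |
| After screening, if eligible | Random selection to video or telephone | Protocol, text after the script |
| Consent form read and sent for signature | Both modes named | Protocol, Consent Procedures and Informed Consent |
| Baseline, then envelope opened | Her allocated arm | Protocol, Methodology |

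**What follows for each Aim 1 measure.**

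1. *Recruitment rate.* The posting acts at the first step, before anyone is counted. The rate through the Box 1 channels is a response to a phone-worded advertisement.
2. *Reasons for declining.* The latest point at which eligible callers learn of video is after screening. Refusals from there on can mix dislike of video with surprise at the change.
3. *Attrition by arm.* All randomised women have passed the disclosure and signed the consent form, and both arms come from the same pool. The posting cannot unbalance the arms, and retention in the video arm is observed directly.
4. *Exit survey.* Participants rate the intervention they received, so this measure does not depend on the posting.

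**A related conflict over refusal data.** The text after Box 1 has all data from a caller who refuses shredded at once and left out of the study. The Follow-up Assessment section says that reasons for refusal will be described, and the SAP says that they will be recorded. As written, the shredding rule could remove the evidence that would help separate dislike of video from other reasons.

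**The case against.** The strongest case for leaving the plan alone is that Box 1 is labelled a sample, invites readers to call for more information, and is one channel among several. Women hear of both modes before written consent, and the verbal consent form, which cannot be seen here, may tell them sooner. A two-arm trial also has a single recruitment rate: even with corrected wording it would measure willingness to be randomised to either mode, not demand for video. All of this stands. It limits the consequence, but it does not make the Box 1 sentence an accurate description of the trial.

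A reader might go further and infer three things that the documents do not support.

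- *That recruitment selects for women who prefer telephone counselling.* This is possible but not shown. The Protocol's background section reports a preference for telephone over in-person counselling and says nothing of telephone against video.
- *That attrition cannot be read as evidence on video.* This does not follow, for the reasons in item 3 of the working. Some disappointment among women assigned to video is conceivable, but no passage establishes it.
- *That Aim 2 is biased against video because missing women count as smoking.* This needs an assumed number of extra dropouts. With 2 to 4 assumed in the video arm, attrition rises by 2/25 = 8 to 4/25 = 16 points. If 30% of those women would have been abstinent (the top of the 28-30% in the pilot among Korean American women), abstinence falls by 0.30 × 2/25 = 2.4 to 0.30 × 4/25 = 4.8 points, or 0.6 to 1.2 women. At the 6-9% that the Protocol cites for people with HIV, the fall is 0.06 × 2/25 = 0.5 to 0.09 × 4/25 = 1.4 points. The direction is uncertain too: telephone-arm women who report abstinence must also do the cotinine test by video call, and refusing it counts as smoking.

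**Conclusion.** The concern holds as a wording error with a limited consequence. Recruitment text in active use misdescribes a trial that assigns half its women to video. Recruitment counts through the Box 1 channels, and refusals after video is disclosed, should be read with caution and may generalise less well to women who would seek video counselling.

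The contradiction between Box 1 and the rest of the Protocol is certain. The size of its effect is unknown, because the documents do not say how many women each channel brings in or how many decline on learning of video. Aim 1 is not invalidated.

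The conclusion assumes that the forwarded e-mail and online post carry the Box 1 text as shown.

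**What to change.** Change the Box 1 sentence to say that counselling is given by video call or by telephone and that chance decides which, in line with what callers are told after screening.

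Reconcile the shredding rule with the plan to record reasons for declining. One way is to keep a tally of refusals and their reasons in anonymous form, noting whether the woman declined after hearing of video, while still destroying identifiable screening data.

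If the current text has already been used, note the date of the change and describe responses before and after it. A formal subgroup analysis by wording would split 50 women too finely to be useful.

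The cost is an IRB amendment and possibly fewer callers once video is mentioned. A fall in response would itself be informative for Aim 1, since it would show interest in the trial as actually offered.

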**The following screening interview script will be used:**

1. Can you speak English? Yes
2. Have you been diagnosed with HIV infection? Yes
3. What kind of medications are you currently taking for HIV infection? (This question is asked as a way to verify HIV infection)
4. How old are you? 18 or older
5. How many cigarettes on average have you been smoking a day? 5 or more cigarettes per day
6. How long have you been smoking? At least for the past 6 months
7. Are you willing to quit smoking within the next four weeks? Yes
8. Are you willing to use nicotine patches? Yes
9. Do you have any active skin disease? No
10. Have you had emotional complications such as feeling anxious and depressed around quitting smoking?  
No. If the caller answers “yes” to this question, we will ask whether the quit attempt was made with or without assistance. We will also ask the severity of the complication(s). If the caller answers that the complications were so distressing and required treatment, she will be excluded from the study.
11. Do you currently receive treatments (counseling and pharmacotherapy) for any of these conditions: Suicidal Ideation, Alcohol Dependence, Schizophrenia, Schizoaffective Disorder, and Bipolar Disorder?  
No
12. Have you ever attempted to kill yourself? No
13. Do you currently use any illegal substances except marijuana (weed)? No
14. Are you pregnant? No
15. Are you currently using any method of birth control? Yes. We will then ask the caller to specify what type of birth control she is currently practicing. If no, we will ask whether the caller is willing to practice birth control during the intervention period (3 months). Only those who use or agree to use an approved form of birth control (e.g., oral medications, condoms, Depo Provera injection, and intrauterine devices) will be accepted into the study.
16. Are you currently breast-feeding? No
17. Do you agree to use birth control pills or devices during the study period? Yes
18. Do you have access to a telephone and an Internet-connected computer? Yes

Women who answer as above will be recruited into the study. They will be informed about the purpose and procedure of the study and then will be given time to ask questions if they have any. Once all questions being answered, [name] (or [name]) will ask them to provide the following contact information: mailing address, e-mail address, at least two connected telephone lines (the participant’s cell phone, home phone or a third phone). [name] (or [name]) will inform that they will be randomly selected to receive smoking cessation counseling either via a video call such as Face-time, Skype and Tango or by telephone. Individuals who are determined to be ineligible will be explained why they are not eligible for the study.

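### Screening item 11 excludes suicidal ideation only when it is being treated, and no script item asks about present ideation, so a caller with untreated ideation can pass.

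*Protocol*

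**What the plan says.** The script stands in the Protocol under III. Methodology, Recruitment Procedures. Three of its 18 items touch mood or suicidality:

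- Item 10 asks about feeling anxious or depressed around quitting. A Yes leads to further questions, and the stated ground for exclusion is treatment: "If the caller answers that the complications were so distressing and required treatment, she will be excluded from the study".
- Item 11 asks about current care: "Do you currently receive treatments (counseling and pharmacotherapy) for any of these conditions: Suicidal Ideation", followed by four other conditions. No qualifies.
- Item 12 asks about past attempts: "Have you ever attempted to kill yourself? No".

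The rule after the script is "Women who answer as above will be recruited into the study".

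A second stage is described in I. Rationale. A diagnostic interview is held for "those who earn a score of 16 or higher on the depression measure or 8 or higher on the Generalized Anxiety Disorder (GAD)-7 Scale". The consequence is "If they meet the diagnostic criteria for any of the disorders based on the DSM-V, they will be excluded". The same paragraph says that women who may have clinical depression or anxiety will be urged to seek treatment.

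The formal exclusion list in IV. Participant does not name suicidal ideation, and its mental-illness criterion also turns on active treatment. Section V. Risks and Benefits sets out a C-SSRS evaluation, an emergency call and later follow-up, to be used if a participant voices suicidal thoughts. Under III. Methodology, the allocation envelope is opened as soon as the baseline assessment is finished.

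**The concern.** The protocol plainly means to screen for suicide risk: it names ideation as a reason not to enrol and rules out any lifetime attempt. As worded, though, the ideation item selects on being in care rather than on the condition. It turns away the woman whose ideation a clinician already knows about and says nothing about the woman whose ideation nobody has assessed. The documents give no reason for this.

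What is at stake is the safety of individual women at entry. The protocol already has an evaluator, a structured instrument and an emergency step, but no answer in the script sets them in motion. The endpoints, the comparison of arms and the sample size of 50 are not affected.

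**Working it through.** There is no figure to reproduce. The check takes two callers through each stage in order. Both have suicidal thoughts now, no past attempt and no quit-related distress that needed treatment, and both give qualifying answers to every other item. Caller A receives no treatment for ideation. Caller B does.

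| Stage | Caller A (untreated) | Caller B (treated) |
|---|---|---|
| Item 10, quit-related distress | Not excluded | Not excluded |
| Item 11, current treatment | Answers No, qualifies | Answers Yes, does not qualify |
| Item 12, past attempt | Answers No, qualifies | Not reached, or No |
| Remaining 15 items | None concerns ideation | None concerns ideation |
| Result of script | Recruited | Turned away |

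Item count: 18 in total; 3 touch mood or suicidality (10, 11, 12), which leaves 18 − 3 = 15; the number asking about present ideation irrespective of treatment is 0.

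Next, what stands between caller A and allocation:

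1. **Formal criteria (IV. Participant).** Ideation is not listed, and the mental-illness criterion depends on treatment. She is not excluded here.
2. **Mood scores (I. Rationale).** If her depression score is below 16 and her GAD-7 is below 8, no interview is prescribed.
3. **Diagnostic interview (I. Rationale).** If either cutoff is met she is interviewed, but the stated ground for exclusion is a depressive or anxiety disorder. If none is diagnosed, no further action is stated. I take the interview to come before allocation, since it can exclude; the text does not say so.
4. **Envelope.** It is opened once baseline is complete. No ideation check is stated before that point.
5. **C-SSRS (V. Risks and Benefits).** This is written for participants and begins when one of them expresses ideation. It is not an entry step.

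The group that can reach allocation without any stated action tied to ideation therefore meets all of these conditions: present, untreated ideation; no past attempt; no quit-related distress that required treatment; and either both scores below their cutoffs or an interview that finds no disorder. The documents give no prevalence for any of these, so the group cannot be sized.

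**The case against.** The strongest reply is that passing the script is not enrolment. The section I stage puts two symptom scores and, where indicated, a diagnostic interview in front of the woman, and the protocol links this to a licensed psychiatric nurse practitioner. Many women with suicidal thoughts might be expected to score above a cutoff. The depression measure is not named and may contain an ideation item; the interview may cover ideation; and the verbal consent form is not in the available text. After allocation, sessions 4 to 6 assess withdrawal symptoms and session 6 takes up low mood and anxiety, so there are scheduled occasions on which the subject could arise. Section V then provides a full response.

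Much of this stands. The second stage narrows the gap, and closure in practice cannot be ruled out. What it does not supply is a stated action on ideation before allocation. The cutoffs act on total scores and the interview on a diagnosis. Even if a questionnaire item asks about suicidal thoughts, no visible text says that anyone acts on that one answer. The counseling sessions come after the envelope and list no ideation question.

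A reader might infer more than the documents support:

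- *That women with untreated ideation will certainly be randomized unnoticed.* The content of the measure and the interview is unseen, so the gap may remain; it is not shown to remain for every such woman.
- *That the intervention worsens ideation.* Nothing in the documents says so, and the point does not need it.
- *That the late timing of repeat mood scores adds to the case.* The SAP places them at 3 and 6 months, but the Protocol's Follow-up Assessment section does not clearly limit them to those visits, and quitting is allowed up to 4 weeks after the first session. The interval is uncertain, and in any case it is beside an entry-screening point.

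**Conclusion.** The point holds in a limited form. The script excludes treated ideation, does not ask about untreated ideation, and recruits on that basis. The section I mood screening reduces the problem but is not tied to ideation, and the section V procedure waits for the participant to speak.

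The weight is moderate: a recommended safety amendment, not a flaw in the trial's inference. No estimate, test or sample-size figure changes. The number of women affected cannot be derived and may be small. The conclusion rests on the available text, on the diagnostic interview preceding allocation, and on there being no unstated practice of reviewing single questionnaire answers. If the depression measure or the interview asks about ideation and a prompt response is prescribed elsewhere, most of the gap would already be covered and the change would mainly align the script with it.

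**What to change.** Add one direct question on current suicidal thoughts to the script, with a stated look-back period. For a Yes:

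1. Take the caller's location and a callback number at once. As written, contact details come only after a passed screen, when staff "will ask them to provide the following contact information: mailing address, e-mail address, at least two connected telephone lines". Recruitment extends to sources such as "AIDS Alabama, University of Mississippi Medical Center" and to online communities, so an emergency step could not be relied on without them.
2. Have the existing section V evaluator complete the C-SSRS before the envelope is opened.
3. If danger is immediate, apply the section V emergency step and do not enrol.
4. Otherwise refer her as section V describes, and randomize only if the evaluator judges it safe.

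State that starting care on this referral does not by itself trigger item 11. Without that sentence, a woman who follows the advice could become ineligible because she followed it.

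The cost is one more sensitive question for each caller, some evaluations by existing staff, a short ethics amendment and possibly some deferred callers, which could slow recruitment to 50. How many callers would be affected cannot be derived. Outcomes and analysis stay as they are, and the rule on shredding screening data need not change.

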#### **IV. Participant**

**Inclusion criteria.** To participate in this study, an individual must be a woman who: (1) is able to speak English, (2) self-reports having been diagnosed with HIV infection, (3) is between the ages of 18 and 75, (4) has smoked at least 5 cigarettes per day for the past 6 months, (5) has access to smartphone and computer (a desktop or laptop) with Internet/wireless, (6) is willing to quit smoking within the next 4 weeks from the first session of counseling, and (7) agrees to use an approved form of birth control during the intervention.

**Exclusion criteria.** Individuals will be excluded based on any of the following criteria: (1) current involvement in other behavioral or pharmacological smoking reduction/cessation programs, (2) being pregnant or lactating, (3) active skin diseases, (4) serious alcohol use problems or current use of any illegal substances, or (5) active treatment for serious mental illness such as schizophrenia and bipolar I disorder.

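### The telephone script that decides recruitment does not apply the protocol's own eligibility criteria, so women whom section IV excludes may pass the screen

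*Protocol*

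**What the plan says.** Eligibility is set out in three places in the Protocol.

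- **The screening script (section III).** It has 18 items, most with a required answer. The text that follows it says "Women who answer as above will be recruited into the study". The items that matter here are "Do you currently receive treatments (counseling and pharmacotherapy) for any of these conditions: Suicidal Ideation, Alcohol Dependence" (item 11, which goes on to name three psychiatric diagnoses), "Do you currently use any illegal substances except marijuana (weed)? No" (item 13), "How old are you? 18 or older" (item 4) and "Do you have access to a telephone and an Internet-connected computer? Yes" (item 18).
- **Section IV, Participant.** It lists seven inclusion and five exclusion criteria, any one exclusion being enough. Among them, a participant "is between the ages of 18 and 75". Exclusion 1 is "current involvement in other behavioral or pharmacological smoking reduction/cessation programs" and exclusion 4 is "serious alcohol use problems or current use of any illegal substances".
- **Section I, Rationale.** A depression score of 16 or more, or a GAD-7 score of 8 or more, leads to a diagnostic interview. Women who then meet DSM criteria for a depressive or anxiety disorder are excluded.

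Consent forms and baseline questionnaires go out after the call (Consent Procedures). The allocation envelope is opened once baseline is finished (section III).

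**The concern.** The rule that admits women and the list that defines who may be admitted are not the same. If staff follow the script as written, some women whom section IV excludes will give every required answer, and others will be turned away for reasons that section IV does not contain.

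This is a feasibility pilot, so the definition of an eligible woman bears directly on what it reports. Under aim 1 the SAP records recruitment and retention rates and the reasons given by eligible women who decline. Under aim 2 it compares abstinence between the arms. With 25 women per arm, each woman counts for 1/25 = 4 percentage points of her arm's rate. That figure only shows how few women each rate rests on; it does not estimate any effect of the mismatch.

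**Working it through.** The plan gives no figure to reproduce, so the check is an item-by-item comparison.

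**Section IV exclusions against the script**

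1. *Other cessation programmes.* No item asks. Item 10 comes nearest, but it concerns emotional complications around quitting. Only after a yes does it ask whether that attempt was assisted, which says nothing about a programme the caller is in now.
2. *Pregnancy or breast-feeding.* Covered by items 14 and 16.
3. *Skin disease.* Covered by item 9.
4. *Alcohol and illegal substances.* Partly covered. Item 11 reaches alcohol only where dependence is being treated; section IV does not depend on treatment, so a woman with a serious untreated problem passes. Item 13 exempts marijuana; section IV has no exemption.
5. *Treated serious mental illness.* Covered in substance by item 11.

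**Other differences**

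- *Age.* Item 4 sets only the lower limit; section IV stops at 75.
- *Devices.* Item 18 asks for a telephone and a computer; section IV requires a smartphone and a computer. This is a minor difference of wording.
- *Birth control.* Item 15 refers to the intervention period, given as 3 months, and agrees with section IV. Item 17 refers to the study period. The conflict is mainly inside the script.
- *Script only.* A lifetime suicide attempt (item 12) and past quit-related complications that needed treatment (item 10) exclude a caller, but neither is in section IV.
- *In neither list.* The section I exclusion for a DSM depressive or anxiety disorder. Item 11 does not name these disorders, item 10 is about distress around quitting, and exclusion 5 is limited to active treatment of serious mental illness.

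**Order of events**

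Section I says the depression and anxiety measures are there for screening, and section III opens the envelope after baseline. A decision before allocation is therefore probably intended. The available text does not say that the diagnostic interview must be finished first. If it came later, the exclusion would fall after randomisation.

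**The case against.** The strongest reply is that the script is not the only gate. The text after it speaks of recruitment, not randomisation; consent and baseline follow. Section IV is mandatory in its own words. Section I says the smoking-related measures cover past cessation treatment, so staff may hold something relevant to exclusion 1 before the envelope is opened. This stands in part, and it is why the claim is that women may pass the telephone screen, not that they will be enrolled. It does not remove the point. Past treatment is not the same as being in a programme now, no available passage describes a second eligibility check on these points, and the instruments are not reproduced. Part of the Protocol was also missing from the text reviewed, so such a check could stand there.

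It is also fair that several differences are slight. Age is asked, so a caller over 75 is easily caught. Willingness to use patches (item 8) follows from an intervention that gives patches to both arms. Treatment for suicidal ideation might fall under the open-ended wording of exclusion 5. The point does not rest on these.

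A reader might infer that the mismatch raises the abstinence rates or biases the comparison of arms. The documents support neither. They give no figure from which an effect on abstinence could be estimated, and the screening takes place before 1:1 allocation.

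**Conclusion.** The concern holds as a contradiction between the recruitment rule and the eligibility criteria. Two points that section IV requires cannot be settled from the script: current participation in another cessation programme, and serious alcohol problems that are not under treatment. On marijuana the two texts disagree outright. Some exclusions stand only in the script, and one stands in neither list. The population to which the recruitment and abstinence rates apply is therefore unclear.

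Confidence in the textual mismatch is high. The number of women affected is unknown and cannot be derived from the documents. The conclusion assumes that the unavailable text holds no later eligibility check on these points. Confidence on the timing of the diagnostic interview is moderate: a reader might infer that women will be excluded after allocation, but the text leaves the order unstated and more likely intends the reverse. The point should be fixed before screening; it does not undermine the design.

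**What to change.** 1. Add a script question on whether the caller is now in another smoking reduction or cessation programme.
2. Have the investigator reconcile section I, the script and section IV into one eligibility list, and make the script ask every item on it. The list should settle alcohol, marijuana, the age limit, devices, the birth-control period, the script-only exclusions and the DSM exclusion. Which clinical rule is right is for the investigator; I take no view.
3. In section III, state that the envelope is opened only after any diagnostic interview is complete and eligibility is confirmed.

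The cost is protocol wording and its ethics approval: one list, a script that follows it, and one sentence on allocation. Allocation waits at most for an interview that is already planned. Sample size and visits do not change.
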